Study Title	A Multi-Center, Randomized, Open-Label Study to Evaluate Symptom Relief and Safety after Using Fexuprazan 40 Mg Compared to Esomeprazole 40 Mg in Patients with Gastroesophageal Reflux Disease (GERD).
Study center(s)	3 Study Center in Indonesia: 1. University of Indonesia Hospital 2. Islam Cempaka Putih Jakarta Hospital 3. Menteng Mitra Afia Jakarta Hospital
Study Period	
 Study duration: Approximately 14 months from IRB approval to completion Study duration for each subject: 8-12 weeks 
 - Screening period: Up to 2 weeks - Treatment period: Up to 4 weeks (unhealed subject will continue additional 4 weeks of treatment) - Follow-up period: For 2 weeks from the last dose
Indication	Gastroesophageal Reflux Disease (GERD) patients
Objective	To evaluate symptom relief and safety after using Fexuprazan 40 mg compared to Esomeprazole 40 mg for patient with Gastroesophageal Reflux Disease (GERD).
Number of subjects	134 subjects
Study Design	A Multi-Center, Randomized, Open label, Double-arm, Controlled study, Investigator Initiated Trial
Study Methodology	
Subjects will be provided a written informed consent to participate in the study and then undergo any screening. If a subject is taking any drug that affects the gastric mucosa at the time of screening, the treatment will be start after washout period of up to 2 weeks. Subjects who meet all of the inclusion criteria and none of the exclusion criteria based on the screening test results will be randomized.
 
Overall, the subjects will receive treatment for a duration of 4 ~ 8 weeks., The subjects will take 1 tablet/capsule of the investigational product (IP) once daily (1 tablet of Fexuprazan 40 mg or 1 capsule Esomeprazole 40 mg according to randomization). Initially, the subject will received the IP for 1 week at Visit 2 (Day 0). Subject will visit the study site at Visit 3 (Day 7 ± 5 days) for early evaluation and will be prescribed for another 3 weeks of IP. Subjects will visit the study site at Visit 4 (Day 28 ± 5 days) to determine healing status through symptom relief. Healed subjects after 4 weeks of treatment will have a Safety Follow-Up (F/U) visit after 2 weeks, while unhealed subjects will continue with an additional 4 weeks of treatment. After unhealed subjects have completed a total of 8 weeks of treatment at Visit 5 (Day 56 ± 5 days), they will have a Safety F/U visit after 2 weeks. (This Safety F/U will be conducted over the phone. If necessary, additional examination and treatment may be performed according to the investigator's judgment.)

Figure 1. Study Schematic

Inclusion Criteria	
Subjects must meet all the following criteria:
 
 1) Male and female adults aged 18 to 60 years at the date of the written informed consent form. 2) Those who had experienced heartburn and/or acid regurgitation confirmed with: 
 ➢ GERD-Q Score >7 and ➢ People who have experienced heartburn symptoms > 3 days within the last 7 days, or ➢ People who have experienced acid reflux (symptom of acid reflux or back flowing of contents from stomach into the esophagus) > 3 days within the last 7 days 3) Those who could understand the provided information and able to fill out the questionnaire and subject diary. 4) Those who voluntarily decided to participate in the study and wrote the informed consent form.
Exclusion Criteria	
[Digestive system related]
 
 1) Those who have been diagnosed with inflammatory bowel disease (Crohn disease, ulcerative colitis, etc.), primary esophageal motility, or pancreatitis. 2) Those who had a surgery to reduce gastric acid secretion or gastric or esophageal surgery (e.g., gastrotomy, mucosal resection, etc.), except appendectomy, cholecystectomy, or endoscopic polypectomy of benign polyps. 3) Those who had warning symptoms of malignant gastrointestinal tract such as odynophagia, severe dysphagia, bleeding, weight loss, anemia, or bloody stool. (But those who have additional warning symptoms besides typical symptoms of gastroesophageal reflux disease may be included if the result of endoscopy for verifying whether to have tumor is negative.) 
[Medical history]
 
 4) Those who had a history of clinically significant disease of hepatic, renal, endocrine, hematologic, or urinary system. 5) Those who had history malignant tumor in the last 5 years. (But in case of malignant tumors except digestive malignant tumor, subjects completely healed for 5 years without recurrence are allowed to enroll.) 6) Those who had a history of psychosis, illegal drug, or alcohol abuse. 7) Those who had a known acquired immunodeficiency syndrome (AIDS) or hepatitis infection, including HBsAg+ or hepatitis C virus (HCV)-antibody-positive or virus carriers. (But the participant may be included in the study if he/she is HCV-RNA-negative). Rapid test screening will be done if there are no previous result. 8) Those who had hypersensitivity or history of clinically significant hypersensitivity reaction to investigational product. 
[Medication history/treatment history]
 
 9) Those who received concomitant prohibition drugs within 2 weeks prior or need continuous treatment during the clinical study* (Those who meet the inclusion criteria following a sufficient wash-out period (2 weeks for NSAIDs with a half-life of > 24 hours) after taking the following drugs can be enrolled) 
 - Non-steroidal anti-inflammatory drugs (aspirin, etc.) and acetaminophen 
 : a low dose of aspirin (≤ 100 mg/day) which has been administered for the purpose of prevention before participating in the study is allowed. : acetaminophen administration is allowed up to 4 g/day and does not exceed 5 days in 4 weeks. - Acid suppressive drugs: Proton pump inhibitors (PPIs), PCAB, H2 receptor antagonists, anti-gastrin agents - Cholinergic drugs, anticholinergic drugs, and antispasmodics - Psychotropic drugs: Antipsychotics drugs, antidepressants, antimanic drugs, antianxiety drugs, and hallucinogenic agents, etc. - Steroids (allowed if used in a local application) - Antithrombotic drugs (antiplatelet drugs and anticoagulants) - Mucoprotective drugs 10) Those who need to take any prohibited concomitant medication during clinical study (Only Antacid and Prokinetic permitted as rescue drug. The use of Antacid and Prokinetic during the study period will be recorded as subject's prior/concomitant medication). 11) Those who took the other investigational product within 4 weeks prior to administration of investigational product. (But it is possible to enroll in the study [i.e., observational study,

	
retrospective study] that doesn't affect this study's efficacy and safety as determined by the investigator.)
 
[Laboratory tests]
 
12) At screening, those who had
 
 ① serum alanine aminotransferase (ALT), aspartate aminotransferase (AST), or total bilirubin levels ≥ 2 X upper limit of normal ② serum creatinine or BUN ≥ 2 X upper limit of normal 
[Others]
 
13) Pregnant or breast-feeding women
 
14) Those who do not consent to use appropriate contraceptive methods during the study.
 
 - Appropriate contraceptive methods for patients or their partners - For Male subject: to use barrier method such as male condom and surgical sterilization such as vasectomy - For Female subject: to use 1) hormonal contraceptive such as Intrauterine system : intrauterine hormone-containing system, implant, injection, contraceptive pills, or 2) non hormonal contraceptive such as Intrauterine system : copper loop, barrier method : female condom, diaphragm or cervical cap, or surgical sterilization : tubectomy. 
15) In the opinion of the investigator, those who were unsuitable for any reason.

Investigational product and mode of administration	
[Investigational Product]
 
 ● Study drug: Fexuprazan tablet 40 mg ● Control drug: Esomeprazole capsule 40 mg 
[Treatment period]
 
 ● Treatment 1: 4 weeks A dose of Study drug or Control drug will be administered orally once daily without regard to meals for 4 weeks. The timing of administration should be kept consistent for each subject. ● Treatment 2: Up to 8 weeks (4 weeks + 4 weeks) Patients who have not been healed after the Treatment 1 of investigational product administration will have an additional 4-weeks of treatment period (Treatment 2) with the same mode of administration. Patients that categorized as a non-healed are those with a GERD-Q score >8.
Efficacy Endpoints	
[Primary efficacy endpoints]
 
 1. Proportions of subjects with symptoms relief at week 4 measured by GERD-Q Score <8 
[Secondary efficacy endpoints]
 
 1. Proportions of subjects with symptoms relief at week 8 measured by GERD-Q Score <8 (Week 8 evaluation will only be applicable to patient receiving treatment 2) 2. Assessment on symptoms based on the diary of subjects 
 - The day to reach complete response (disappearance of heartburn, acid regurgitation, or heartburn/acid regurgitation for 7 consecutive days) after the first IP administration. - Proportions of subjects without the major symptoms (heartburn, acid regurgitation, or heartburn/acid regurgitation) for first 7 days, 4 weeks, and 8 weeks after the first IP administration. - Proportions of days free of major symptoms (heartburn, acid regurgitation, or heartburn/acid regurgitation) for first 7 days, 4 weeks, and 8 weeks after the first IP administration (including all daytime, nighttime, and daytime/nighttime) 3. Assessment on symptoms of reflux disease (GERD-Q) 
 - Changes from baseline in frequency by major symptom after 7 days, 4 weeks and 8 weeks. 4. Assessment of Quality of Life (GERD-HRQL: GERD-Health related quality life) 
 - Changes from baseline in the total score of GERD-HRQL after 7 days, 4 weeks and 8 weeks. (Week 8 evaluation will only be applicable to patient receiving treatment 2) 
[Exploratory endpoints]
 
Assessment on symptoms based on the diary of subjects.
 
 - Proportions of subjects who have not been awakened during sleep for heartburn or acid regurgitation for first 3 days, 7 days, 4 weeks, and 8 weeks (or based on the day Investigator's need) after the first IP administration.

	
 - Proportions of subjects who have relieved from chronic cough for first 3 days, 7 days, 4 weeks, and 8 weeks (or based on the day Investigator's need) after the first IP administration daytime and nighttime. - Proportions of subjects who have relieved from irritating feeling in the throat for full 3 days, 7 days, 4 weeks, and 8 weeks (or based on the day Investigator's need) after the first IP administration daytime and nighttime. 
(Week 8 evaluation will only be applicable to patient receiving treatment 2)

Safety Endpoints	
 1. Adverse events 2. Vital signs (blood pressure [diastolic/systolic], pulse rate, respiratory rate, and body temperature) 3. Physical examination (head to toe general physical examination) 4. Laboratory tests (hematology, blood chemistry, blood coagulation, urinalysis, liver function, renal Function)
Statistical Analysis Method	
[Primary efficacy endpoints] The proportions of subjects with symptoms relief by Week 4 and their 95% confidence intervals will be provided by group. The proportions of subjects with symptoms relief by Week 4 will be calculated as the cumulative symptoms relief by using the results at the time of final observation including the Withdrawal visit. To compare the control group and study group, the lower bound of the 2-sided 95% confidence intervals will be obtained by using the Chi Square test or Fisher's Exact test method. If this lower bound is greater than the non-inferiority margin of -0.1, the study group will be judged to be non-inferior to the control group.
 
[Secondary efficacy endpoints]
 
 1. The proportions of subjects with symptoms relief by Week 8 and their 95% confidence intervals will be provided by group. The proportions of subjects with symptoms relief by Week 8 will be calculated as the cumulative symptoms relief by using the results at the time of final observation including the Withdrawal visit. To compare the control group and study group, the lower bound of the 2-sided 95% confidence intervals will be obtained by using the Chi Square test or Fisher's Exact test method. If this lower bound is greater than the non-inferiority margin of -0.1, the study group will be judged to be non-inferior to the control group. (Week 8 evaluation will only be applicable to patient receiving treatment 2) 2. Assessment on symptoms based on the diary of subjects. 
 - Complete Response (disappearance of heartburn, acid regurgitation, or heartburn/acid regurgitation for 7 consecutive days) is defined as the symptom score of 0 for 7 consecutive days for the first time after the first dose, and the survival time is defined as the time to reach Complete Response (CR) after the first IP administration. Kaplan-Meier plots will be drawn by treatment group, and the medians and their 2-sided 95% confidence intervals will be presented. To compare the control group and study group, the log-rank test will be used. - The number of subjects without any heartburn, acid regurgitation, or heartburn/acid regurgitation for the first 7 days, full 4 weeks, and full 8 weeks from the first IP administration, the proportion (%) of these subjects and its 95% confidence interval will be presented by treatment group. To compare the control group and study group, the 2-sided 95% confidence intervals and p-value will be obtained by using the Chi Square test or Fisher's Exact test method. - Descriptive statistics (mean, standard deviation, median, minimum, and maximum) of the proportions of days free of any heartburn, acid regurgitation, or heartburn/acid regurgitation for the first 7 days, full 4 weeks, and full 8 weeks from the first IP administration will be presented for daytime, nighttime, and daytime/nighttime by group. For comparison between treatment groups, an ANCOVA model will be applied with treatment group as a treatment effect. The results of ANCOVA model will be summarized as the LSM differences between the study group and the control group, the corresponding 2-sided 95% confidence interval, and p-value. 
(Week 8 evaluation will only be applicable to patient receiving treatment 2)


3. Assessment on symptoms of reflux disease using GERD-Q

Descriptive statistics (mean, standard deviation, median, minimum, and maximum) for the changes from baseline in frequency at the first 7 days, 4 weeks, and 8 weeks will be presented by time point. For the changes from baseline in variables measured at the first 7 days, 4 weeks, and 8 weeks after the IP administration, an ANCOVA model including treatment group as treatment effect, and baseline value will be applied. The results of ANCOVA model will be summarized as the least squares mean (LSM) and standard error by treatment group, the LSM differences between the study group and the control group, the corresponding 2-sided 95% confidence interval, and p-value.

(Week 8 evaluation will only be applicable to patient receiving treatment 2)

4. Quality of life assessment using GERD-HRQL

Descriptive statistics (mean, standard deviation, median, minimum, and maximum) for the changes from baseline in the total score of quality of life at the first 7 days, 4 weeks, and 8 weeks will be presented by time point. For the changes from baseline in variables measured at the first 7 days, 4 weeks, and 8 weeks after the IP administration, an ANCOVA model including treatment group as treatment effect, baseline values, and stratification factor (based on dominant symptoms in inclusion criteria: experiencing heartburn, regurgitation, or both more than >3 days in the last 7 days) as covariate will be applied. The results of ANCOVA model will be summarized as the least squares mean (LSM) and standard error by treatment group, the LSM differences between the study group and the control group, the corresponding 2-sided 95% confidence interval, and p-value.

(Week 8 evaluation will only be applicable to patient receiving treatment 2)

[Exploratory endpoints]

Assessment on symptoms based on the diary of subjects.

- The proportions (%) of subjects who have not been awakened during sleep for heartburn or acid regurgitation for the first 7 days, full 4 weeks, and full 8 weeks after the first IP administration and its 95% confidence interval will be presented by treatment group. To compare the control group and study group, the 2-sided 95% confidence intervals and p-value will be obtained by using the Chi Square test or Fisher's Exact test method.
- The proportions (%) of subjects who have relieved from chronic cough for the first 7 days, full 4 weeks, and full 8 weeks after the first IP administration and its 95% confidence interval will be presented by treatment group. To compare the control group and study group, the 2-sided 95% confidence intervals and p-value will be obtained by using the Chi Square test or Fisher's Exact test method.
- The proportions (%) of subjects who have relieved from foreign body sensation for the first 7 days, full 4 weeks, and full 8 weeks after the first IP administration and its 95% confidence interval will be presented by treatment group. To compare the control group and study group, the 2-sided 95% confidence intervals and p-value will be obtained by using the Chi Square test or Fisher's Exact test method.

(Week 8 evaluation will only be applicable to patient receiving treatment 2)

[Safety Endpoints]

All adverse events (AEs) will be standardized according to MedDRA version 21.0 (or higher). The frequency and percentage of subjects with at least 1 AE (or adverse drug reaction) will be presented by treatment group, and the 95% confidence intervals will be also presented. The frequency and percentage of subjects who are withdrawn due to serious adverse events or AEs will be presented and the listings will be provided.

The descriptive statistics (mean, standard deviation, median, minimum, maximum, etc.) will be presented for continuous data, such as hematology, blood chemistry results, and vital signs by treatment group and visit; the frequency and percentage will be presented for categorical data, such as urinalysis and physical examination by category.

[Schedule of Study Activities]

	Screening (wash-out)	Treatment 1			Safety F/U ¹⁾	Treatment 2 (Unhealed Subject after 4 Weeks of Treatment)	Safety F/U ¹⁾	Withdrawal Visit ¹²⁾
Visit	Visit 1 ¹⁾	Visit 2	Visit 3	Visit 4	Visit 4-1	Visit 5	Visit 5-1	
Schedule	Day-14 ~	Day 0	Day 7	Day 28	Day 42	Day 56	Day 70	
Window	-	-	±3day	±5day	±5day	±5day	±5day	
Informed consent	O							
Demographic survey	O							
Assessment on symptom questionnaire (GERD-Q) ²⁾	O	O	O	O		O ¹³⁾		O ^{*)}
Quality of Life assessment (GERD-HRQL)		O	O	O		O ¹³⁾		O ^{*)}
Medical and surgical history ³⁾	O	O						
Prior/concomitant medications ⁴⁾	O	O	O	O	O	O	O	O ¹²⁾
Vital signs ⁵⁾	O	O	O	O	O ¹¹⁾	O ¹³⁾	O ¹¹⁾	O ¹²⁾
Physical examination	O	O	O	O	O ¹¹⁾	O ¹³⁾	O ¹¹⁾	O ¹²⁾
Laboratory tests ^{6),7)}	O			O	O ¹¹⁾	O ¹³⁾	O ¹¹⁾	O ¹²⁾
Pregnancy test ^{6),8)}	O	O						
Inclusion/exclusion criteria ⁹⁾		O						
Prescription of IPs ¹⁰⁾		O	O	O ¹³⁾				
Return of IPs and check of treatment compliance ¹⁰⁾			O	O		O ¹³⁾		O ¹²⁾
Distribution of subject diary ¹⁰⁾			O	O	O ¹³⁾			
Collection of subject diary ¹⁰⁾			O	O		O ¹³⁾		O ¹²⁾
Adverse events			O	O	O	O	O	O ¹²⁾

- 1) Visit 1 and Visit 2 can be conducted on the same day.
- 2) Eligibility of subjects will be assessed based on the results from Visit 2 (GERD-Q result from Visit 1 will be used as the eligibility criteria). However, the results may be replaced with the test results obtained within 7 days prior to Visit 2, if available.
- 3) Gastrointestinal medical history and surgical history will be investigated at Visit 1 regardless of the time of previous occurrence and, for other medical history and surgical history, only those which occurred within 6 months from screening or are ongoing at screening and baseline will be investigated.
- 4) For prior medications, information on drugs administered within 4 weeks from the date of the written consent at Visit 1 will be collected. (Only Antacid and Prokinetic permitted as rescue drug)
- 5) Vital signs: After resting in a sitting position for 5 minutes or longer, blood pressure (diastolic/systolic), pulse rate, and body temperature will be measured.
- 6) The relevant tests can be replaced with the test results obtained from the same institution within 2 weeks from Visit 1, if available.
- 7) Laboratory tests will be conducted to check the inclusion/exclusion criteria and assess the safety (Visit 1, Visit 4, Visit 5, Withdrawal visit, and Safety F/U). At Visit 1, a re-test may also be conducted once according to the investigator's judgment and, in such a case, evaluation will be based on the result of re-test.

① Hematology	WBC with differential count (neutrophil, lymphocyte, monocyte, eosinophil, basophil), RBC, hemoglobin, hematocrit, platelets
② Blood Chemistry	Random blood glucose, ureum, uric acid, AST, ALT, creatinine, total bilirubin
③ Blood Coagulation test	PT, INR, APTT
④ Urinalysis	pH, specific gravity, albumin, bilirubin, glucose, urobilinogen, ketone, nitrite, occult blood, microscopy (urine RBC, urine WBC)

- 8) Pregnancy test will be performed with serum or urine pregnancy test will be performed at Visit 1. (Women who medically do not have child-bearing potential are exempt from the pregnancy test). If Visit 1 and Visit 2 are conducted on the same day, another pregnancy test (serum or urine test) should be conducted prior to IP administration even if the test result within 2 weeks before the date is available.
- 9) Eligibility of subjects will be assessed based on the results from Visit 2 (However GERD-Q result from Visit 1 will be used as the eligibility criteria).
- 10) Subjects who have not symptoms relief at Visit 4 will be prescribed the investigational product for treatment 2, and subject diary will be distributed to them. At Visit 5, treatment compliance will be checked, and subject diary will be collected only from those who have undergone Treatment 2.
(#: Subject diary completion will be checked at Visit 3, and appropriate training on diary keeping will be performed on the phone, if necessary.)
- 11) The Safety F/U will be conducted as a telephone visit within 2 weeks (\pm 5 days) from Last day of Visit 4 and Visit 5 only in subjects who complete all protocol-specific treatments, and the subjects may visit for additional tests or treatments based on the investigator's judgment.
- 12) If a subject decides to discontinue participation or is withdrawn from the study before completion, the Withdrawal visit procedures will take place within 2 weeks from the withdrawal decision. At the Withdrawal visit, the unused IPs or empty packaging will be returned, and the subject diary will be collected. However, assessment of Gastroesophageal Reflux Disease Questionnaire (GERD-Q)^{*)} and quality of life questionnaire (GERD-HRQL)^{*)} must be performed. If the patient refused to visit, above two Questionnaires can be done by telephone call and the document should be written on the EMR by the investigator.
- 13) Subjects who have not been healed after the Treatment 1 of investigational product administration will have an additional 4-weeks of treatment period (Treatment 2) with the same mode of administration.

[Abbreviations and Definition of Terms]

ADR	Adverse drug reaction
AE	Adverse event
AIDS	Acquired immune deficiency syndrome
ALT	Alanine aminotransferase, alanine
ANCOVA	Analysis of Covariance
APA	Acid pump antagonist
AST	Aspartate transaminase, aspartate
ATC	Anatomical therapeutic chemical
BUN	Blood urea nitrogen
BPOM	Indonesia Food and Drug Authority

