6.2 Administration Route and Method of Investigational Products

For maximum 4 weeks from the next day of investigational product prescription, 1 tablet/capsule will be administered orally once daily without regard to meals. Tablets/capsules should be taken at a regular time, if possible.

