7.1 Overall Study Methodology

Screening Period

Subjects will provide written informed consent to participate in the study and then undergo any screening. Subjects who meet all the inclusion criteria and none of the exclusion criteria based on the screening test results will be included into the study.

Treatment Period

The subject will receive the IP consumed once daily for 1 week at Visit 2 (Day 0). Subjects will have a site visit 1 week after IP administration and prescribed the IP for another 3 weeks at Visit 3 (Day 7 ± 3 days). Subjects will visit the study at Visit 4 (Day 28 ± 5 days) to determine healing status by Gastroesophageal Reflux Questionnaires (GERD-Q).

Subjects who have not been healed at Visit 4 (Day 28 ± 5 days) will have an additional IP administration period for 4 weeks and then visit the study site at Visit 5 (Day 56 ± 5 days) to determine healing status.

If, a subject withdrawn during the treatment period will visit the study site within 2 weeks from the withdrawal decision and undergo the Withdrawal visit procedures. However, they will not be conducted if the subject refuses them.

Follow up Period

Subjects will have a Safety F/U visit within 2 weeks (± 5 days) from the day when healing is confirmed. (However, this visit will be carried out by a telephone visit. If necessary, additional examination and treatment may be performed according to the investigator's judgment.)

[figure not shown]

Figure 2. Study Schematic

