7.2.2 Administration Method

For maximum 8 weeks from the next day of investigational product dispensing, 1 tablet/capsule will be administered orally once daily without regard to meals. Tablets/Capsules should be taken at a regular time.

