8.3.13 Investigational product administration

For maximum 8 weeks from the next day of investigational product dispensing, 1 tablet/capsule will be administered orally once daily without regard to meals. Tablets/Capsules should be taken at a regular time, if possible. At each visit after the administration of the IP all subjects should return the unused IP prescribed at the previous visit and empty packaging.

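### Treatment 1 dosing is limited to 4 weeks but Visit 4 may fall as late as Day 33, so off-drug days can enter the 7-day GERD-Q recall; the Visit 3 window is also stated in two ways

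*Combined protocol and SAP*

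**What the plan says.** **Visit 3 window.** The synopsis (Study Methodology) schedules "Visit 3 (Day 7 ± 5 days) for early evaluation and will be prescribed for another 3 weeks of IP". Section 7.1 has subjects "prescribed the IP for another 3 weeks at Visit 3 (Day 7 ± 3 days", and the schedule tables in the synopsis and in section 8.2 also show ±3 days.

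**Supply.** One week of drug is given at Visit 2 (Day 0) and three further weeks at Visit 3. Quantities are stated as durations, never as tablet or capsule counts. Section 8.3.13 adds that at each visit "all subjects should return the unused IP prescribed at the previous visit and empty packaging".

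**Length of dosing.** For Treatment 1 the synopsis specifies dosing "once daily without regard to meals for 4 weeks". Section 6.2 has it run "For maximum 4 weeks from the next day of investigational product prescription". Section 7.2.2 gives the same instruction as "For maximum 8 weeks from the next day of investigational product dispensing", and section 8.3.13 repeats the 8-week figure. No section says that dosing continues until the Visit 4 assessment.

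**Primary assessment.** Section 7.1: "Subjects will visit the study at Visit 4 (Day 28 ± 5 days", which allows Days 23 to 33. The primary endpoint is GERD-Q below 8 at that visit (section 8.4.1.1). The questionnaire in Attachment 2 asks about the preceding 7 days.

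**The concern.** A visit window is harmless when treatment runs up to the visit. Here treatment has a fixed length and the visit does not. A subject who attends late, but within the window, can report on days when no drug was taken, and those days count in the score that decides relief.

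The endpoint sits close to its threshold. A symptom-free subject already scores 6, so a few symptomatic days after the last dose can turn relief into non-relief. The measure would then reflect visit timing as well as treatment.

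The two Visit 3 windows are a separate and simpler fault. A site that follows the synopsis could see a subject on a day that the schedule table treats as out of window, and the date of Visit 3 also governs when the second supply starts.

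**Working it through.** **Inputs.** First dose on the day after dispensing, so Day 1 (6.2, 7.2.2, 8.3.13). Supply of 1 week and then 3 weeks, taken once daily: 7 + 21 = 28 doses if packs hold an exact count (an assumption). Visit 3 on Days 4-10 (7.1, 8.2). Visit 4 on Days 23-33 (7.1). Recall of 7 days (Attachment 2).

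**Recall window.** For Visit 4 on Day w, the recall covers Days w-7 to w-1 if the visit day is not counted, or w-6 to w if it is. With last dose on Day L, the off-drug days are w-1-L or w-L, bounded between 0 and 7.

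**1. The plan's own schedule.** Visit 3 on Day 7 and Visit 4 on Day 28: doses on Days 1-7 and 8-28, so L = 28. Off-drug recall days: 0 on either count.

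**2. Visit 3 on Day 7, Visit 4 late.** The 4-week limit gives L = 28 even if the subject holds spare tablets.

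| Visit 4 | Visit day not counted (w-1-28) | Visit day counted (w-28) |
|---|---|---|
| up to Day 28 | 0 | 0 |
| Day 29 | 0 | 1 |
| Day 30 | 1 | 2 |
| Day 33 | 4 | 5 |

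**3. Early Visit 3, exact-count packs, leftovers returned.** Visit 3 on Day 4: doses on Days 1-4, 3 tablets returned, 21 doses on Days 5-25, so L = 25. An on-time Day 28 visit then has 28-1-25 = 2 or 28-25 = 3 off-drug recall days. If leftovers are kept, L = 28 and the count is 0.

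**4. Late Visit 3, exact-count packs.** Visit 3 on Day 10: the first 7 doses end on Day 7. Days 8-9 are undosed, or Days 8-10 if the next-day rule applies to each resupply. That is 2-3 days, which can touch the GERD-Q and GERD-HRQL completed at Visit 3 and the diary endpoints that span those days.

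**5. Effect on the score.** Items 3 and 4 give 3 points each at 0 days, so a symptom-free subject scores 0+0+3+3+0+0 = 6. Heartburn on 2 days adds 2, giving 8, which is non-relief. If one of those days also brings epigastric pain, item 3 falls from 3 to 2 and the total is 7, which is still relief. The effect therefore does not run in one direction only.

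**6. Does the compliance rule catch it?** Section 13.5 makes compliance below 80% a major deviation. Visit 3 on Day 7 and Visit 4 on Day 33: 28/28 = 100% of supplied doses, or 28/33 = 84.8% of days. Visit 3 on Day 4 and Visit 4 on Day 28: 25/28 = 89.3%. All stay in the per-protocol set, which is the primary analysis set.

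**7. Scale.** With the 53 evaluable subjects per arm in section 9.4.2, one reclassified subject moves that arm's rate by 1/53 = 1.9 percentage points, against a 10-point margin. This is a unit of scale, not an estimate of effect.

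**The case against.** The strongest reply is that the protocol states durations and not pack sizes. Counting returned tablets at every visit fits surplus supply as well as missed doses, and quantities may be fixed in dispensing documents that are not part of this text. That stands against the early and late Visit 3 cases, which hold only for exact-count packs. It does not remove the late Visit 4 case, because the 4-week limit in the synopsis and section 6.2 ends dosing on Day 28 even with tablets in hand. The 8-week figure in sections 7.2.2 and 8.3.13 can be read as covering both treatment periods. It does not say whether Treatment 1 runs on to a late visit.

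A second reply is that a fixed 4-week course with an ordinary visit window is a legitimate choice. It is, but a 7-day recall then needs a visit that falls by the end of dosing, and the window allows 5 days more.

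A third is that daily diary entries on drug intake and the pill counts already show undosed days. They would identify such days. They do not prevent them, and no rule acts on them.

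A reader might also infer more than the text supports:

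- **All 7 recall days off drug.** This needs the earliest Visit 3, the latest Visit 4, exact-count packs and surrendered leftovers together. It is a corner case.
- **Off-drug days at a Day 12 Visit 3.** This relies on the ±5 window, which three other places contradict.
- **Bias against one arm, or a threat to the non-inferiority conclusion.** Supply and windows are the same in both arms. The documents give neither the frequency of late visits nor the speed at which symptoms return, so neither bias nor cancellation can be shown.
- **An equal problem in Treatment 2.** The arithmetic is similar: "will have an additional IP administration period for 4 weeks and then visit the study site at Visit 5 (Day 56 ± 5 days", so dosing from Day 28 ends on Day 56 and the visit may fall on Day 61. But this is a secondary endpoint, and at the planned relief rates it concerns about 67 × 0.115 + 67 × 0.06 = 11.7 subjects. Dosing to Day 61 would also exceed the plan's 8-week maximum.

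**Conclusion.** The point holds as a minor one. The Visit 3 window conflict is plain on the page. The recall problem follows from the stated 4-week limit, the Day 33 end of the Visit 4 window and the 7-day recall. After an on-time Visit 3 it is confined to Visit 4 on Days 29-33, with 4-5 of 7 recall days off drug at the extreme and none on the nominal schedule.

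The 2-3 off-drug days before an on-time Visit 4, and the 2-3 undosed days before a Day 10 Visit 3, rest on exact-count packs. The first also needs leftovers to be returned and not re-issued. The number of subjects affected and any between-arm effect cannot be computed from the documents. What can be said is that some primary scores may be misclassified for a reason that is cheap to prevent.

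**What to change.** 1. Correct the synopsis to ±3 days for Visit 3.
2. State that Treatment 1 dosing continues once daily until the Visit 4 assessment, and reword the 4-week limits in the synopsis and section 6.2 to allow the visit window.
3. If existing packs do not already cover it, supply 10 doses at Visit 2 and, at Visit 3, enough to reach Day 33. That is 33 minus the visit day: 29, 26 or 23 doses for Visit 3 on Day 4, 7 or 10. This leaves no off-drug recall day at Visit 4 in any of the 7 × 11 = 77 in-window combinations of Visit 3 and Visit 4, and it closes the gap before a late Visit 3.
4. Leave the 8-week limit unchanged unless the sponsor chooses to extend it, but say how it applies after a late Visit 4. Dosing to Day 33 plus 28 more days is 61 days. Under an 8-week limit of 56 days, Treatment 2 would have 56 - 33 = 23 days.
5. Keep the primary analysis unchanged.

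**Cost.** Extra doses are (10 + 29) - 28 = 11 per subject at most, or 11 × 134 = 1,474 in all, many of them returned unused. After an on-time Visit 3 the figure is (10 + 26) - 28 = 8. Late attenders receive up to 5 more days of treatment, so exposure at the primary assessment follows the visit date and is no longer a fixed 4 weeks.
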